1.3 Other Agents

Usual Care

Usual care at the UCSD Moores Cancer Center palliative care clinic includes the use of stimulant laxative prophylaxis (up to 8 tablets/day of senna or up to 30mg/day of bisacodyl) and/or constipation treatment (primarily osmotic laxatives such as polyethylene glycol plus stimulant laxatives). Stimulant laxatives (senna or bisacodyl) are used daily regardless of bowel movement as prophylaxis of OIC. If OIC occurs despite optimal dosing of stimulant laxative, then a standard dose of polyethylene glycol (17 grams per day) is used for treatment of OIC until it resolves.

1.4 Rationale

OIC is a common symptom in patients with cancer-related pain and requires burdensome self-titration of laxatives for prophylaxis and treatment. Consequently, naloxegol may have an important role in this setting. Naloxegol has been evaluated in relieving OIC with cancer patients in a randomized, double blind, placebo-controlled trial over 4 weeks with a 12-week extension phase. However, accrual was challenging and the trial was closed early.¹⁴ Given the complexity of cancer and its treatment, a key first step is to determine if evaluating naloxegol versus standard of care is feasible in the management of OIC in this setting.

2.0 STUDY OBJECTIVES

2.1 Primary Objective

To evaluate the feasibility of naloxegol 25mg in the treatment of OIC in comparison to usual care.

We hypothesize that feasibility, defined as more than 70% of selected study subjects completing all study related procedures, will be achieved.

2.2 Secondary Objectives

1. To determine the frequency of naloxegol versus usual care on OIC as defined by ≤ 3 bowel movements per week.
2. To evaluate naloxegol versus usual care on stool quality using the Bristol Stool Scale (BSS).²
3. To describe the adverse events associated with naloxegol when administered daily in this patient population and to compare the adverse events associated with Naloxegol with adverse events observed with usual care, using the National Cancer Institute Common Terminology Criteria for Adverse Events (NCI CTCAE) version 4.03.³
4. To evaluate health related quality of life utilizing the Patient Assessment of Constipation Symptoms (PAC-SYM)⁴ and Patient Assessment of Constipation Quality of Life (PAC-QOL).⁵
5. To evaluate changes in patient reported pain using the Brief Pain Inventory-Short Form (BPI-sf).⁶

2.3 Exploratory Objectives

1. To evaluate laxative compliance with weekly pill counts.
2. To evaluate healthcare resource utilization as defined by the number of emergency room visits, hospitalizations, telephone encounters, and EPIC mychart encounters regarding signs/symptoms associated with constipation between the two arms.
3. To determine patient preference to continue naloxegol in the optional 12-week extension.

2.4 Endpoints

The primary endpoint on this study is defined as completion of all study drug over the first 4 weeks of study treatment (initial and crossover treatment phases).

Secondary endpoints include number of bowel movements per week, as captured on the Patient bowel movement diary (**Appendix F**), stool quality as measured by the Bristol Stool Scale (**Appendix G**), safety defined as the rate of drug-related adverse events experienced assessed according to the NCI's CTCAE v4.03 toxicity criteria, and health related quality of life and pain measures as assessed by the PAC-SYM, PAC-QOL, and BPI-sf, within the first 4 weeks of study treatment (see **section 9.3.3**).

Exploratory endpoints will include drug administration compliance as measured by weekly pill counts by a member of the study team, healthcare resource utilization as defined by the number of number of emergency room visits, hospitalizations, telephone encounters, and EPIC mychart

encounters related to signs and symptoms of constipation, and patient preference (yes/no) for naloxegol to treat OIC as defined by choice of participation in the optional extension phase of the study.

3.2 Exclusion Criteria

Subjects meeting any of the exclusion criteria at baseline will be excluded from study participation.

1. Patient has received any of the following agents within 3 days prior to Study Day 1 and/or are planned to receive throughout the duration of the study: opioid antagonist and mixed agonist/antagonist (e.g. pentazocine, buprenorphine, nalbuphine, naloxone/naloxone combinations, naltrexone/naltrexone combinations, methylnaltrexone, alvimopan), a strong CYP3A4 and/or P-gp inhibitor, a moderate CYP3A4 and/or P-gp inhibitor, and/or a strong CYP3A4 inducer (see **Appendices B and C**).
2. Patient currently receiving or planned to receive concurrent total parenteral nutrition.
3. Patient currently receiving or planned to receive concurrent use of metoclopramide (or other GI prokinetic agents which can potentially slow the GI tract motilities) or use within 24 hours prior to study treatment (elimination $t_{1/2}$ 6 hours).
4. Patient is at high risk for bowel perforation.
5. Patient has constipation that was not primarily caused by opioids, as determined by the investigator.
6. Patient has a condition that may have affected the permeability of the blood-brain barrier (e.g., known brain metastases, meningeal metastases, brain injury, multiple sclerosis, recent brain injury, uncontrolled epilepsy).
7. Patient has clinically active diverticular disease.
8. Patient has a history of irritable bowel syndrome, signs of active GI bleeding, acute surgical abdomen, bowel stents, indwelling peritoneal catheter, mechanical GI obstruction, fecal impaction, or fecal ostomy.
9. Patient has motility/neurologic disorders including autonomic failure (spinal cord lesions, tumor invasion of nerves) and/or poorly controlled endocrine/metabolic disorders (hypercalcemia, hypokalemia, diabetes, hypothyroidism), as determined by the investigator.
10. Patient has uncontrolled cancer pain despite analgesic therapy.
11. Patient has a severe organ impairment or uncontrolled medical disorder that would, in the investigator's opinion, impair the ability to receive study treatment (i.e., uncontrolled diabetes, severe acute or chronic renal failure, severe pulmonary disease, severe hepatic impairment or active, uncontrolled infection, psychiatric illness/social situations that would limit compliance with study requirements).
12. Patient has any other condition that, in the opinion of the investigator, may impact the absorption of oral medications.
13. Patient is pregnant or nursing. There is a potential for congenital abnormalities and for this regimen to harm nursing infants.

4.0 TREATMENT PLAN

4.1 Study Design

This is a single center, randomized, open-label crossover study. We anticipate recruitment of approximately 60 total study participants at the UCSD Moores Cancer Center. Study participants will be recruited across all oncology disease teams. Potential participants will be identified in weekly palliative care or disease team patient triage meetings.

In order to meet eligibility for participation, a patient must be ≥ 18 years old, have histologically confirmed cancer, an ECOG performance status ≤ 3 , serum creatinine $\leq 1.5 \times$ institution's ULN, corrected serum calcium level ≤ 10.5 mg/dL, and life expectancy ≥ 6 months. Qualifying subjects must have documented, confirmed OIC which is defined as ≤ 3 bowel movements and/or Bristol Stool Scale (BSS) 1-2 more than 25% of defecations¹ during the preceding week.

Patients will be excluded if constipation is not primarily due to treatment with opioids or if they have signs or symptoms of a mechanical GI obstruction, fecal impaction, acute surgical abdomen, fecal ostomy, indwelling peritoneal catheter, bowel stents, signs of active GI bleeding, or are high risk for bowel perforation. Any patient with a past medical history of irritable bowel syndrome, motility/neurologic disorder, poorly controlled endocrine/metabolic disorder, any condition that may have affected the permeability of the blood-brain barrier, and/or uncontrolled cancer pain despite analgesic therapy will also be excluded from participation. Finally, in order to participate, patients cannot receive concurrent total parenteral nutrition and/or metoclopramide, and must discontinue use of the following medications within 3 days of Study Day 1: opioid antagonist, mixed antagonist, a strong CYP3A4 and/or P-gp inhibitor, a moderate CYP3A4 and/or P-gp inhibitor, and/or a strong CYP3A4 inducer (**Appendices B,C**).

The primary objective of this study is to evaluate the feasibility of naloxegol 25mg in the treatment of OIC in comparison to usual care, defined as completion of all study drug over 4 weeks, including initial and crossover treatment phases.

Secondary objectives will seek to determine the effect of naloxegol versus usual care on OIC, to evaluate naloxegol versus usual care on stool quality (BSS), to describe the adverse events associated with naloxegol when administered daily in this patient population (NCI CTCAE v4.03), to evaluate health related quality of life (PAC-SYM and PAC-QOL), and to evaluate changes in patient reported pain (BPI-sf).

Exploratory objectives will evaluate laxative compliance, healthcare resource utilization, and patient preference to continue naloxegol in the optional 12-week extension period.

Following informed consent, patients will have the following procedures completed to confirm eligibility: physical exam with vital signs, height, and weight, ECOG performance status, complete blood count, comprehensive metabolic panel, and a serum pregnancy test (women of child-bearing potential only). During this screening period, patients will also complete baseline PAC-SYM, PAC-QOL and BPI-sf questionnaires. To confirm OIC, patients will be asked about their frequency of bowel movements in the last week and asked to recall the average BSS that they have experienced. Upon confirmation of all eligibility criteria and within 72 hours of the initial dose of study treatment, patients will be randomized in a 1:1 ratio to either Arm A or Arm B by block randomization. Randomization will be performed by CTRI using a randomization package in the software R (blockrand)^{15,16}. The CTRI office will provide the study coordinator with prestuffed envelopes numbered 1-62. In the envelope, a paper will indicate the treatment assignment. One envelope will be assigned to each patient by the study coordinator in order of accrual. The number on the envelope will become the patient number and will be the identification number on all study documents. Individual patient randomization arm must be assigned prior to the patient being treated on study. The study coordinator will contact IDS once subject randomization arm has been confirmed.

REGIMENT DESCRIPTION				
Treatment Phase	Arm A	Arm B	Schedule	Cycle Length
Initial	Single 25 mg tablet Route: Orally, on an empty stomach 1 hour before breakfast or 2 hours after first meal of the day	Usual Care: stimulant laxative (i.e. up to 8 tablets/day of senna or up to 30mg/day of bisacodyl) ± osmotic laxative (e.g., polyethylene glycol)	Daily, Days 1-14	2 weeks (14 days)
Cross-Over	Usual Care: stimulant laxative ± osmotic laxative	Single 25 mg tablet Route: Orally, on an empty stomach 1 hour before breakfast or 2 hours after first meal of the day	Daily, Days 18-31	2 weeks (14 days)
Extension (Optional)	Single 25 mg tablet Route: Orally, on an empty stomach 1 hour before breakfast or 2 hours after first meal of the day	Single 25 mg tablet Route: Orally, on an empty stomach 1 hour before breakfast or 2 hours after first meal of the day	Daily, Days 32-116	12 weeks (84 days)

Wash out: Based on an elimination half-life of 10 hours, a 3-day washout period (50 hours or 5 half lives, approximately 48 hours) will occur before crossover.

Optional 12-week extension: Patients on Arms A and B will have the option to continue on naloxegol at 25 mg daily for an additional 12-week extension phase upon completion of initial and crossover treatment phases.

On Study Days 1, 18, 32, patients will undergo physical exam with vital signs and weight, ECOG performance status, complete blood count, comprehensive metabolic panel, and will receive a new treatment supply. Pill counts and study drug accountability will also be performed.

During initial and crossover treatment periods, patients will complete daily questionnaires and diaries, including the patient study drug diary, patient bowel movement diary, patient medication use diary, BSS, and BPI-sf. Concomitant medications and adverse event data will also be collected daily. All adverse events will be graded according to NCI CTCAE v4.03. Weekly assessments will include patient completion of the PAC-SYM questionnaire. Bi-weekly assessments include patient completion of the PAC-QOL questionnaire. Pill counts will be performed weekly throughout the duration of study, and may be performed via telephone call by a member of the study team if no in-person visit has occurred with the patient during a previous week.

During the optional extension phase, patients will be asked to return to clinic every 28 days for a new supply of naloxegol, return of any unused naloxegol, review of the previous month's study drug diary, pill count and completion of PAC-SYM, PAC-QOL, and BPI-sf. Concomitant medications and adverse event data will continue to be collected daily.

Within 28 days after the patient's final dose of treatment on study, patients will undergo an end-of-study visit during which a final pill count and study drug accountability will be performed. Final PAC-SYM, PAC-QOL, and BPI-sf questionnaires will also be completed. Adverse event information will be collected until 28 days following final dose of study treatment.

4.2 Treatment Administration

Patients in Arm A will receive a single daily dose of 25mg naloxegol for the 2-week initial treatment period, followed by a 3-day washout period and 2-week crossover treatment period in which the patient will receive the treating physician's usual care for OIC using a stimulant laxative ± rescue medication.

Patients in Arm B will receive the treating physician's usual care for OIC using a stimulant laxative ± rescue medication for the 2-week initial treatment period, followed by a 3-day washout period and 2-week crossover period in which the patient will receive a single daily dose of 25mg naloxegol.

Patients on Arms A and B will have the option to continue on naloxegol at 25 mg daily for an additional 12-week extension phase upon completion of initial and crossover treatment phases.

Patients will be instructed to take naloxegol on an empty stomach at least 1 hour prior to the first meal of the day or 2 hours after the meal. Tablets must be swallowed whole, and not crushed or chewed by the subject. Subjects will also be instructed to avoid consumption of grapefruit or grapefruit juice as this is a potent inhibitor of the CYP3A4 enzyme.

Patients will also be instructed to complete a daily study drug diary during the treatment phases when naloxegol is being administered. Patients will be asked to bring their completed study drug diary with them during each visit for review with a member of the study team.

If the patient misses their daily morning dose of naloxegol and it has been less than 2 hours since the missed dose, they will be instructed to take naloxegol as soon as it is remembered on the same day. If it has been more than 2 hours since missing a dose, the patient will be instructed to skip the dose for that day not to make up that dose. If the patient vomits after taking a dose, he/she will be instructed not to repeat the dose or attempt to make up that dose.

If a patient takes more than the assigned daily dose of naloxegol, they should be monitored closely for evidence of opioid withdrawal symptoms and reversal of central analgesic effects. In cases of known or suspected overdose, symptomatic treatment as well as monitoring of vital functions should be performed. In cases of severe intoxication, intensive care procedures are recommended. Close medical supervision and monitoring should be continued until the patient recovers.

Any adverse events or serious adverse events resulting from known or suspected overdose will be reported according to instructions in **Section 7.6** of the protocol.

Treatment with naloxegol does not require that any pre-treatment parameters be met prior to dispensing and/or administration.

4.3 Pre-Medications

There are no required pre-medications on this study.

4.4 Permitted Concomitant Therapy

Throughout the study, investigators will be encouraged to maintain a patient's baseline pain control regimen, with dose adjustments made as clinically indicated throughout participation in the study. It is anticipated that the majority of participants will be receiving a long-acting opioid for control of background pain and an immediate-release opioid as needed ("prn") for breakthrough pain, although some may be receiving only a short-acting opioid on a scheduled basis. Changes in the opioid regimen may be made to ensure appropriate pain control. Any changes to the maintenance opioid dosing regimen will be recorded. Concomitant non-opioid analgesics will be permitted, but investigators will be encouraged to maintain such drugs at stable doses on-study as possible.

It is recognized that some patients may have their pain managed by physicians who are not co-investigators on this study. In these cases, patients will be asked to notify their UCSD treating investigator or study team member of any changes in a patient's pain control regimen.

Patients may take laxatives during the screening period of the study, but must discontinue use of laxatives at least 3 days prior to Study Day 1. In addition, patients may take an opioid antagonist, mixed antagonist, a strong CYP3A4 and/or P-gp inhibitor, a moderate CYP3A4 and/or P-gp inhibitor, and/or a strong CYP3A4 inducer during the screening period of the study, but must discontinue use of these agents at least 3 days prior to Study Day 1. During the initial and cross over treatment periods, if a bowel movement has not occurred within at least 72 hours, a patient may take bisacodyl as a laxative rescue medication in addition to the dosage of Naloxegol or stimulant laxative. If after a minimum of 72 hours, the patient has not experienced a BM, he/she may take bisacodyl rescue therapy (10-15 mg dose or 2-3 tablets at a time). If the patient remains constipated, bisacodyl rescue therapy may be repeated up to two additional times, as necessary, each 10-15 mg dose separated by 12 hour intervals. It is recommended that the bisacodyl tablets be taken either at bedtime or before breakfast. Of note, both the usual care arm and rescue therapy will use standard doses of bisacodyl (5-15 mg per day). If after 3 doses of rescue therapy, the patient still has not experienced a bowel movement, the investigator may prescribe a one-time use of an enema. The timing of administration of this therapy will be noted on the patient medication use diary. If these secondary interventions fail, the patient should be discontinued from the study and referred for additional medical evaluation. The investigator should recommend initiation of any therapy deemed most appropriate.

Other medication, which is considered necessary for the patient's safety and well-being, may be given at the discretion of the investigator, and will be recorded on the patient medication use diary as well as the concomitant medications case report form.

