those observed in healthy volunteers. Mean T_{max} was less than 1.7 hours across dose groups and dosing days, indicating naloxegol was rapidly absorbed. Mean terminal half-life values were similar across dose levels (5 to 50 mg), ranging from 14.1 to 20.3 hours. The primary route of naloxegol elimination is via hepatic metabolism, with renal excretion playing a minimal role. Naloxegol is a sensitive substrate of CYP3A4 enzyme and a substrate of P-gp transporter, and CYP3A4 is the major CYP enzyme responsible for the metabolism of naloxegol. Concomitant use with dual P-gp or strong CYP3A4 inhibitors, or moderate CYP3A4 inhibitors, significantly increases naloxegol plasma concentrations (**Appendices B and C**). Conversely, concomitant use with a strong CYP3A4 inducer results in decreased plasma concentration.

Two multi-center, placebo-controlled 12-week, intent-to-treat, Phase III studies have been completed to evaluate naloxegol efficacy in the treatment of OIC. The primary endpoint in both studies was the proportion of patients who showed a pre-specified response, defined as at least 3 spontaneous bowel movements per week and at least a 1 spontaneous bowel movements per week increase over baseline for at least 9 out of the 12 treatment weeks and 3 out of the last 4 treatment weeks during the double-blind treatment period. Symptom ratings for straining, stool consistency, and complete bowel movements were consistent with improvements in spontaneous bowel movement frequency and latency. In both studies, for the naloxegol 25 mg group compared with placebo, the primary and all key secondary endpoints achieved statistical significance with $p<0.025$ in each case. Compared to placebo, naloxegol 25 mg/day had a higher percentage of patients responding (40-44% vs. 29%), shorter median time to first post-dose spontaneous bowel movement (6-12 vs. 36-37), and greater improvement in OIC symptoms. In terms of safety data from these Phase III studies, the incidence of severe adverse events (SAEs) was similar across treatment groups. Pneumonia was the most frequently reported SAE overall, with no notable imbalance in frequency across treatment groups.

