5.1.13.4 Bristol Stool Scale (BSS)

Subjects will rate stool consistency through completion of the Bristol Stool Scale (BSS) after each bowel movement. The BSS was developed by Heaton at the University of Bristol and was first published in the Scandinavian Journal of Gastroenterology in 1997 (Lewis and Heaton 1997). It is a medical aid designed to classify feces into seven categories (**Appendix G**), as follows:

- 1 - Separate hard lumps, like nuts (hard to pass)
- 2 - Sausage-shaped, but lumpy
- 3 - Like sausage, but with cracks on its surface
- 4 - Like a sausage or snake, smooth and soft
- 5 - Soft blobs with clear cut edges (passed easily)
- 6 - Fluffy pieces with ragged edges, a mushy stool
- 7 - Watery, no solid pieces

Subjects will be asked to document a BSS score at the time of OIC confirmation and daily during the initial and crossover treatment periods. This score takes approximately 1 minute to complete.

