6.3 Efficacy Assessment

The efficacy of treatment with naloxegol versus treatment with usual care will be evaluated by the number of bowel movements per week, as captured on the Patient Bowel Movement Diary, and the stool quality as defined by the Bristol Stool Scale. These measures will be assessed within the first 4 weeks of study treatment.

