9.3.3 Secondary Endpoints

Secondary outcome measures are the effect of naloxegol versus usual care on; bowel movements per week, stool quality using the BSS,² occurrence and grade of AEs using the NCI CTCAE version 4.03,³ health related quality of life utilizing the PAC-SYM⁴ & PAC-QoL,⁵ and changes in patient reported pain using the BPI-sf.⁶

For variables in the secondary aim, we plan to use generalized linear mixed effects models to determine the impact of naloxegol on each endpoint over the course of 2 weeks for the initial treatment and crossover treatment phases of the study, achieved by including treatment group as a categorical covariate, and including a categorical time effect to account for a potential period effect. Counts of bowel movements per week will be assessed using a Poisson model. Stool quality (BSS, 7 point Likert-type scale), PAC-SYM (5 point Likert-scale), and PAC-QOL (5 point Likert-scale) will be assessed using an ordinal logistic model. The two parts of the BPI-sf (Intensity of pain and inference of pain) are calculated as the mean of several questions; as such they will be assessed as a continuous outcome with possible transformation for skewness if necessary.

To control for the multiple comparisons, a Bonferroni-Holm (e.g. Stepwise Bonferroni) method will be applied to the combined secondary and exploratory analyses, using an omnibus $\alpha = 0.05$.

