Appendix F. Patient Bowel Movement Diary

Laxation Diary

Protocol No.	Participant No.	Participant Initials	Treatment Phase/Day No.	Date Diary Completed
UCSD XXXXXX				

Instructions for completion:

[figure not shown]
- Please remember to complete this diary daily while participating in this study.
- Record each bowel movement that you have throughout the day on a separate line. For each bowel movement recorded, please list the time and Bristol Stool Scale type (see opposite side of this diary for description of types).
- At the end of each day, please record the total number of bowel movements for that day in the space provided.
- If you did not have any bowel movement throughout the day, please leave all spaces for time and Bristol Stool Scale Type blank, and record "0" in the space for total number of bowel movements.

Time of bowel movement (hh:mm) am/pm	Bristol Stool Scale Type (Type 1-7)
Total number of bowel movements in the last 24 hours? _____	
Please sign when the diary has been completed at the end of each day and return to the study coordinator during your next clinic visit.	
Patient Signature: _____ Date: _____	

version dated 25SEP15

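### The secondary bowel-movement count includes movements that follow rescue bisacodyl or an enema, and no planned analysis separates them or compares rescue use

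*Combined protocol and SAP*

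**What the plan says.** Section 2.4 defines the first-listed secondary endpoint as the "number of bowel movements per week, as captured on the Patient bowel movement diary". Section 6.3 says efficacy is "evaluated by the number of bowel movements per week, as captured on the Patient Bowel Movement Diary", together with stool quality. The diary form in Appendix F tells the patient: "Record each bowel movement that you have throughout the day on a separate line". It has no field for rescue. Section 5.1.13.4 adds that "Subjects will rate stool consistency through completion of the Bristol Stool Scale (BSS) after each bowel movement", so stool-quality scores also include movements after rescue.

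Under Section 4.4, once at least 72 hours have passed without a movement, "a patient may take bisacodyl as a laxative rescue medication in addition to the dosage of Naloxegol or stimulant laxative". Up to three rescue doses are allowed, 12 hours apart. If these fail, "the investigator may prescribe a one-time use of an enema". The rule is the same in both periods.

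Section 9.3.3 says "Counts of bowel movements per week will be assessed using a Poisson model", within a mixed model containing treatment and period. It has no term, exclusion or sensitivity analysis for rescue. Rescue laxative use is recorded daily (Section 5.1.13.2), but Section 9.3 never compares it between treatments. Section 1.2 reports that the earlier phase III trials required "at least 3 spontaneous bowel movements per week" as part of their response definition; this trial's endpoint does not carry over the word spontaneous.

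**The concern.** Rescue is triggered by failure to have a movement. A treatment that leaves patients constipated reaches 72 hours more often, calls for more rescue, and is then credited with the movements that rescue produces. A difference in rescue use, itself evidence about the treatments, is turned into extra counts on the worse side and disappears from view.

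At stake is how the secondary efficacy estimate is read. Section 9.1 presents this trial as preparation for a large phase III crossover study, so an estimate of unknown rescue content could mislead the planning of that trial.

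**Working it through.** **Stated figures.** The documents give no effect size, variance, power or rescue rate for the movement count, so no plan figure can be reproduced for this endpoint. The one power statement, in Section 9.2, concerns completion. With n = 50, 70% against 85% and a one-sided exact test, the critical value is 41 of 50, the exact alpha is 0.040 and the power is 79.1%, in line with the stated 80%. It does not depend on bowel movements.

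**Inputs from the protocol.** 72-hour trigger, up to three doses 12 hours apart, 14 days per period.

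**Assumed inputs.** Unaided movements are Poisson, at 2 per week on the worse treatment and 3 on the better (true ratio 1.5). Rescue is taken in a fraction q of the episodes that reach 72 hours. Each dose succeeds with probability p = 0.5 to 0.8, and the movement comes 10 hours later. Enemas are ignored.

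**Formula.** Let L be the unaided weekly rate and λ = L/168 the hourly rate. If rescue would produce a movement at time R after the last one, the mean gap is (1/λ)(1 − E[e^(−λR)]). Hence the long-run all-movement rate is

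L / (1 − qS), with S = Σ p(1−p)^k e^(−λ(82+12k)), k = 0, 1, 2.

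For p = 0.5, S = 0.3055 at L = 2 and 0.1812 at L = 3. For p = 0.8, S = 0.3628 and 0.2197.

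| Uptake q | p = 0.5: rates, ratio | p = 0.8: rates, ratio |
|---|---|---|
| 0.25 | 2.17 v 3.14, 1.45 | 2.20 v 3.17, 1.44 |
| 0.50 | 2.36 v 3.30, 1.40 | 2.44 v 3.37, 1.38 |
| 1.00 | 2.88 v 3.66, 1.27 | 3.14 v 3.84, 1.23 |

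A 14-day period leaves slightly less room for rescue than the long run. Simulating 14 days gives about 1.45, 1.38 and 1.26 to 1.30; other reasonable dosing details move these by 0.01 to 0.03.

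**On the difference scale.** A 14-day simulation with varying patient rates and every rescue successful was run for 2 v 3, 2.5 v 3.5, 3 v 4 and 2 v 4 per week. The difference shrinks by 2–3% at 25% uptake, 7–8% at 50% and 18–25% at 100%.

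**Unequal uptake.** By the formula, the ratio returns to its true value when q(naloxegol) × S(naloxegol) = q(usual care) × S(usual care). With naloxegol as the better treatment and 50% uptake under usual care, that needs 0.5 × 0.3055/0.1812 = 0.84 or 0.5 × 0.3628/0.2197 = 0.83 under naloxegol. Above that, the ratio is inflated. The difference is more sensitive. In the simulation of 2.5 v 3.5 with 50% usual-care uptake, shrinkage vanishes at a naloxegol uptake between 0.55 and 0.60; at 0.75 the all-movement difference is 1.12, against 0.96 rescue-free.

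**Excluding movements soon after rescue.** Dropping movements within 24 hours of rescue also drops some that would have come unaided, and more of them on the worse treatment. At full uptake a true 1.5 becomes about 1.6, so this count errs the other way.

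**The case against.** The strongest reply is that rescue belongs to the treatments being compared. Section 4.2 writes optional rescue medication into its description of usual care, and Section 1.3 has polyethylene glycol added when a stimulant laxative fails. For a comparison of strategies as delivered, counting all movements is legitimate. This stands. It is why the all-movement count should stay, but the plan never says that this is the question being asked.

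A second objection is that an exclusion rule is uneven. It removes movements after bisacodyl rescue but keeps those after polyethylene glycol added for failure under usual care, which could tilt the contrast against naloxegol. This also stands, and it limits the exclusion count to a supportive role.

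Third, the data may not support an hour-based window. Section 4.4 says the timing of administration will be noted in the medication diary, but the Appendix E form has columns for date, times per day, dose and reason, with no clock time. Bisacodyl is also a usual-care drug, so identifying rescue rests on the reason column.

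A reader might infer that the planned analysis is certainly biased towards no difference. The documents do not support that. Rescue is optional, the trial is open-label, and the usual-care period already contains laxatives, so uptake may differ in either direction. The spontaneous-movement precedent does not settle it either: those trials were placebo-controlled, and the protocol does not define the term.

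**Conclusion.** The gap is real. As written, the secondary count (and the stool-quality scores) includes movements that follow rescue, and no analysis separates them or compares rescue use. Shrinkage is the expected direction if rescue is taken equally readily in both periods: a true ratio of 1.5 would appear as about 1.45, 1.38 or 1.26 to 1.30 at 25%, 50% or 100% uptake. These figures rest on assumed Poisson movements, rates of 2 and 3 per week, and a dose success of 0.5 to 0.8. The full-uptake values are the extreme of the range and should not be quoted alone. With markedly higher uptake in the naloxegol period, the shrinkage could vanish or reverse.

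It would also go too far to read this as a flaw in the trial's main result. The primary endpoint is completion, which this does not touch. The point is a low-cost improvement to the interpretation of a secondary endpoint.

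**What to change.** In Section 9.3.3:

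1. Keep the all-movement count and state that it compares treatment strategies including rescue.
2. Pre-specify a comparison of rescue days per period between treatments, using the date and reason columns of the medication diary.
3. Add a supportive count that excludes movements on the calendar day of, or the day after, a Section 4.4 rescue dose or enema. If a time field is added to Appendix E, a 24-hour window can be used instead. Report this as a sensitivity analysis and note that it somewhat overcorrects.
4. Tabulate polyethylene glycol added for failure under usual care, since those movements stay in the count.

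The cost is one extra secondary analysis, the rescue-use comparison and a table, from diaries already collected; the time field is optional. The weak point is reliance on the reason entry to tell rescue bisacodyl from usual-care bisacodyl. Dose will not do this reliably, because the bisacodyl amounts within Section 4.4, and between it and the usual-care description in Section 4.1, do not agree; those passages must be reconciled. No change to the rescue rule or the primary analysis is needed.
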